5.3.1 Dose Specifications

IMRT has been a standard of care in the U.S. beginning in 2005 and is now widely used in practice. Use of H&N IMRT in RTOG protocols (and associated QA) was begun in 2005 in RTOG 0522, as an optional technique. At the close of the accrual phase, approximately 90% of cases enrolled on 0522 (>800 patients) were treated with IMRT. Oropharynx cases comprised 70% of the study population.

IMRT will be delivered in 30-35 fractions over 6-7 weeks, 5 fractions weekly. The primary tumor and involved nodes (CTV1) will typically consist of a 0.5-1.5 cm expansion of the gross tumor volume (GTV) to cover potential local invasion and will be prescribed 2 Gy/fraction, total 55-70Gy. High-risk sub-clinical disease sites, which include possible local subclinical infiltration at the primary site (primary site CTV2) and first echelon nodes, which are not clinically or radiographically involved (nodal CTV2), should be expanded by 3-5 mm to create PTV2. PTV2 should receive 1.6 Gy/fraction to a total dose of 52.8 Gy to 56 Gy. Lower-risk targets (PTV3) (such as neck nodal levels which are not first echelon nodes and are not adjacent to levels containing grossly involved nodes) will be prescribed 50-52.5 Gy. If the low neck is treated, the preferred technique is to treat with isocentric matching AP or AP-PA fields with larynx block, matched to the IMRT portals just above the arytenoids. The dose will be 2 Gy per fraction prescribed to 3 cm depth to a total dose of 50 Gy in 25 daily fractions. Whole-neck IMRT is allowed. This can be achieved by either boosting the low neck field with an additional 16 Gy in 8 fractions, by an AP or AP-PA fields, or by planning the whole neck using IMRT. In cases of gross involvement of the vallecula or low neck, whole-neck IMRT should be considered. Whole-neck IMRT may also be considered if level VI is considered to be at risk due to gross involvement of level IV nodes. All plans must be normalized such that 95% of the volume of the PTV is covered with prescription dose.

In cases of weight loss >10% or significant shrinkage of lymphadenopathy during therapy, it is recommended that the immobilization mask will be adjusted or re-made in order to preserve adequate immobilization, and that a repeated simulation CT be performed to assess the dose distributions in the current anatomy. Whether or not a new IMRT plan will be generated is at the discretion of the treating physician. If a new plan is made, the targets should be the same as those used for the initial plan. The new CT dataset should be used for IGRT image registration when the patient's shape changes significantly.

5.3.2 Compliance Criteria

Treatment breaks must be clearly indicated in the treatment record along with the reason(s) for the treatment break(s). Treatment breaks, if necessary, ideally should not exceed 5 treatment days at time and 10 treatment days total. Treatment breaks should be allowed only for resolution of severe acute toxicity and/or for intercurrent illness and not for social or logistical reasons. Any treatment break(s) exceeding 2 treatment days for reasons other than toxicity/illness will be considered a protocol deviation. The following define compliance:

Overall RT treatment time:

- ≤ 52 days (compliant)
- > 52 days (non-compliant)
- Up to 57 days for non-medical reasons (such as holiday, machine breakdown) as determined by the treating radiotherapy physician

Missed treatments due to holidays or logistic reasons can be compensated for by delivering an additional BID treatment during the week, OR treating on the Saturday or Sunday of that week, OR adding to the end of treatment. These additions will not be considered non-compliance.

5.3.3 Radiation Therapy Toxicity/Adverse Events

Grade 3-4 (CTCAE, v. 4.0) therapy-induced mucositis and/or dysphagia, which are enhanced by cisplatin, are expected to develop in about two-thirds of patients. Nutritional evaluation prior to the initiation of therapy for a prophylactic gastrostomy (PEG) tube placement is highly recommended. Placement of a feeding tube should be recorded, as should use of a feeding tube during and after treatment (e.g. greater than or less than 50% of nutrition by tube). Other common radiation adverse events include: fatigue, weight loss, regional alopecia, xerostomia, hoarseness, transient ear discomfort, dysgeusia, and skin erythema and desquamation within the treatment fields. Less common long-term treatment adverse events include: hypothyroidism, loss of hearing, chronic swallowing dysfunction requiring permanent feeding tube, and cervical fibrosis. Much less common radiation adverse events include: mandibular osteoradionecrosis, and cervical myelopathy (< 1% with restriction of spinal cord dose to ≤ 45 Gy).

5.3.4 R.T. Quality Assurance Reviews

We will use several approaches to ensure H&N IMRT quality assurance (QA) including H&N anatomic atlases, site and machine certification of H&N IMRT, and individual case reviews. The department performs routine radiation review and QA as part of standard of care.

5.3.5 Technical Factors, Localization, Simulation, and Immobilization

Patients must have an immobilization device (e.g. Aquaplast mask) made prior to treatment planning CT scan. The treatment planning CT scan should be performed with IV contrast so that the major vessels of the neck are easily visualized. The treatment planning CT scan must be performed with the immobilization device and in the treatment position. Slice thickness should be 0.3 cm.

5.3.6 Treatment Planning/Target Volume

Planning Target Volumes (PTVs): In general, the PTV should not go outside of the skin surface; if it does exceed the skin surface, the application of bolus material over this portion of the PTV may be considered if it is judged clinically that the skin is at risk but

is generally not recommended. In general, the CTV-to-PTV expansion (without IGRT) should not exceed 10 mm. In general, the CTV-to-PTV expansion (with IGRT) should not exceed 5 mm.

5.3.7 Definition of Normal Tissues/Organs at Risk (OARs)

NOTE: Only the parts of the normal tissues/organs at risk outside the PTVs will be considered for dose optimization purposes.

Spinal Cord: The cord begins at the cranial-cervical junction (i.e. the top of the C1 vertebral body). Superior to this is brainstem and inferior to this is cord. The inferior border of the spinal cord is at approximately T3-4 (i.e., just below the lowest slice level that has PTV on it). The spinal cord shall be defined based on the treatment planning CT scan. In addition, however, a Planning Risk Volume (PRV) spinal cord shall be defined. The PRV_{cord} = cord + 5 mm in each dimension. This is irrespective of whether or not IGRT is used.

Brainstem: The inferior most portion of the brainstem is at the cranial-cervical junction where it meets the spinal cord. For the purposes of this study, the superior most portion of the brainstem is approximately at the level of the top of the posterior clinoid. The brainstem shall be defined based on the treatment planning CT scan. In addition, however, a Planning Risk Volume (PRV) brainstem shall be defined. The PRV_{brainstem} = brainstem + 3 mm in each dimension.

Lips and Oral Cavity: These should be contoured as 2 separate structures as the goal is to keep the lip dose much lower than the oral cavity dose. The oral cavity will be defined as a composite structure consisting of the anterior $\frac{1}{2}$ to $\frac{2}{3}$ of the oral tongue/floor of mouth, buccal mucosa, and palate.

Parotid Glands: Parotid glands will be defined based on the treatment planning CT scan.

Cervical Esophagus: This will be defined as a tubular structure that starts at the bottom of the oropharynx and extends to the thoracic inlet.

Glottic/Supraglottic Larynx (GSL): This will be defined as a “triangular prism shaped” volume that begins just inferior to the hyoid bone and extends to the cricoid cartilage inferiorly and extends from the anterior commissure to include the arytenoids. This includes the infrahyoid but not suprathyoid epiglottis.

Mandible: This includes the entire bony structure of the mandible from TMJ through the symphysis.

Unspecified Tissue Outside the Targets: This will be defined as tissue located between the skull base and thoracic inlet that is not included in either the target volumes or the normal tissues described above.

5.3.8 IMRT Dose Prescription to PTVs

The goal is for 95% of the planned PTV to receive ≥ 2 Gy with a minimum dose (cold spot). It is recognized that portions of the PTV close to the skin may receive significantly less. This is acceptable as long as cold spots within PTV1 do not exist at a depth deeper than 8 mm beneath the skin.

For planning prioritization and priorities in dose coverage, in the final plan, PTV1 will be the highest priority target structure. PTV2 and PTV3, if applicable, will be ranked in the IMRT planning as lower priority than PTV1m although usually at a higher priority than normal structures other than spinal cord and brain stem.

5.3.9 Doses to Normal Structures

Spinal Cord: The PRVcord should not exceed ≤ 50 Gy to any volume in excess of 0.03 cc (approximately 3 mm x 3 mm x 3 mm).

Brainstem: The PRV brainstem (as defined in Section 6.4.2.2) should not exceed 52 Gy to any volume in excess of 0.03 cc (approximately 3 mm x 3 mm x 3 mm).

Lips: Reduce the dose as much as possible. The mean dose should be < 20 Gy.

Oral Cavity: Reduce the dose as much as possible. The mean dose should be < 30 Gy for the non-involved oral cavity. Efforts should also be made to avoid hot spots (> 60 Gy) within the noninvolved oral cavity.

Parotid Glands: In most cases, it will be easier to spare one parotid than the other. The treatment planning goal will be for this individual parotid gland to receive a mean dose of < 26 Gy.

Contralateral submandibular gland: If contralateral level I is not a target, aim to reduce mean contralateral submandibular gland to < 39 Gy.

Mandible: Reduce the dose as much as possible. Hot spots within the mandible should be avoided. It is recommended that maximum dose within the mandible be < 66 Gy.

Unspecified Tissue Outside the Targets: No more than 1cc of unspecified tissue outside the targets can receive 74 Gy or more.

5.3.10 Prioritization for IMRT Planning

1. Spinal Cord
2. Brainstem
3. PTV1
4. PTV2 (if applicable)
5. PTV3 (if applicable)

6. a. Oropharynx, b. Parotid gland contralateral to primary tumor site
7. a. GSL, b. Esophagus
8. a. Lips, b. Oral Cavity
9. a. Parotid gland ipsilateral to primary tumor site, b. Mandible
10. Unspecified tissue outside the targets

5.4 General Concomitant Medication and Supportive Care Guidelines

Concomitant use of anti-emetics should follow institutional guidelines for highly emetogenic chemotherapeutic regimens. Additional guidance can be found at www.nccn.org. Additional supportive measures for toxicity from chemotherapy and radiation are at the investigators discretion, and not restricted.

Placement of a gastrostomy tube (PEG or PFG) before treatment begins is recommended to optimize nutrition and hydration during combined therapy.

Aggressive oral and skin care, and analgesics are recommended.

Use of G-CSF (Filgrastim) or other growth factors is not anticipated for any treatment arm of this protocol. However, if the use of a growth factor is judged to be necessary in the supportive care of a patient by the treating physician, its use should be carefully documented on eCRFs, and should follow NCCN guidelines. Additional guidance can be found at www.nccn.org.

5.5 Duration of Therapy

In the absence of treatment delays due to adverse event(s), treatment will continue for 7 weeks or until one of the following criteria applies:

- Disease progression,
- Intercurrent illness that prevents further administration of treatment,
- Unacceptable adverse event(s),
- Patient decides to withdraw from the study, or
- General or specific changes in the patient's condition render the patient unacceptable for further treatment in the judgment of the investigator.

5.6 Duration of Follow Up

Patients will be followed for 2 years after completion of chemoradiation or until death, whichever occurs first, for toxicity and PFS. Following resolution of toxicity and completion of primary endpoint assessment by PI and study team, long-term follow-up of 5 years will be performed by the Kentucky Cancer Registry. Patients removed from study for unacceptable adverse event(s) will be followed until resolution or stabilization of the adverse event.

5.7 Criteria for Removal from Study

Patients will be removed from study when any of the criteria listed in Section 5.5 applies. The reason for study removal and the date the patient is removed must be documented in the Case Report Form.

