11.1.1 Definitions

Evaluable for toxicity. All patients will be evaluable for toxicity from the time of their first treatment with cisplatin.

Evaluable for objective response. Only patients who have measurable disease present at baseline, have received at least one cycle of therapy, and have had their disease re-evaluated will be considered evaluable for response. These patients will have their response classified according to the definitions stated below. (Note: Patients who exhibit objective disease progression prior to the end of cycle 1 will also be considered evaluable.)

Evaluable Non-Target Disease Response. Patients who have lesions present at baseline that are evaluable but do not meet the definitions of measurable disease, have received at least one cycle of therapy, and have had their disease re-evaluated will be considered evaluable for non-target disease. The response assessment is based on the presence, absence, or unequivocal progression of the lesions.

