11.1.4.3 Evaluation of Best Overall Response

The best overall response is the best response recorded from the start of the treatment until disease progression/recurrence (taking as reference for progressive disease the smallest measurements recorded since the treatment started). The patient's best response assignment will depend on the achievement of both measurement and confirmation criteria.

For Patients with Measurable Disease (i.e., Target Disease)				
Target Lesions	Non-Target Lesions	New Lesions	Overall Response	Best Overall Response when Confirmation is Required*
CR	CR	No	CR	≥ 4 wks Confirmation**
CR	Non-CR/Non-PD	No	PR	≥ 4 wks Confirmation**
CR	Not evaluated	No	PR	
PR	Non-CR/Non-PD/not evaluated	No	PR	
SD	Non-CR/Non-PD/not evaluated	No	SD	Documented at least once ≥ 4 wks from baseline**
PD	Any	Yes or No	PD	no prior SD, PR or CR
Any	PD***	Yes or No	PD	
Any	Any	Yes	PD	

* See RECIST 1.1 manuscript for further details on what is evidence of a new lesion.

** Only for non-randomized trials with response as primary endpoint.

*** In exceptional circumstances, unequivocal progression in non-target lesions may be accepted as disease progression.

Note: Patients with a global deterioration of health status requiring discontinuation of treatment without objective evidence of disease progression at that time should be reported as “*symptomatic deterioration*.” Every effort should be made to document the objective progression even after discontinuation of treatment.

For Patients with Non-Measurable Disease (i.e., Non-Target Disease)Non-Target Lesions	New Lesions	Overall Response
--	--------------------	-------------------------

CR	No	CR
Non-CR/non-PD	No	Non-CR/non-PD*
Not all evaluated	No	not evaluated
Uequivocal PD	Yes or No	PD
Any	Yes	PD

* ‘Non-CR/non-PD’ is preferred over ‘stable disease’ for non-target disease since SD is increasingly used as an endpoint for assessment of efficacy in some trials so to assign this category when no lesions can be measured is not advised.

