13.2 Sample Size/Accrual Rate

The primary objective of this study is to see if cisplatin delivered weekly results in fewer cisplatin-related toxicities and improved tolerability compared to cisplatin administered every 3 weeks. Both groups will still receive standard of care radiation therapy in addition to cisplatin. Assuming historical rates of 80% toxicities for patients receiving XRT + cisplatin every 3 weeks [10, 32-34], with 36 patients per arm we will have 80% power based on a Fisher's exact test to detect a decrease in toxicity rate to 50%, assuming a one-sided level of significance equal to 0.05. Conservatively assuming a 10% loss to follow-up, we will recruit 80 total patients for at least 72 analyzable.

Based on the Cancer Research Informatics SRF incidence tables for SCCHN from 2010-2014, **there were an average of 125 patients seen per year at MCC** that would be eligible for this trial based on tumor stage and tumor site. If even 33% of these subjects met all criteria and agreed to participate, we anticipate this study would be completed in 2 years. Our HN CCART has an excellent track record of accrual to clinical trials in this subset of SCCHN, thus we feel that this estimate is conservative and that it is possible that we could accrue faster than predicted.

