13.7 Reporting and Exclusions

13.7.1 Evaluation of Toxicity

All patients will be evaluable for toxicity from the time of their first treatment with cisplatin or radiation.

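### Section 5.7 makes every reason for stopping treatment a removal from study, contradicting the protocol's own follow-up requirements, and the analysis plan has no rule for the incomplete outcomes that could result

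*Combined protocol and SAP*

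**What the plan says.** Section 5.5 governs therapy: "treatment will continue for 7 weeks or until one of the following criteria applies". The five criteria are progression, intercurrent illness, unacceptable adverse events, the patient's decision to withdraw from the study, and a change in condition judged by the investigator. Section 5.7 reuses the list for a different purpose: "Patients will be removed from study when any of the criteria listed in Section 5.5 applies". It also requires a removal date and reason on the case report form.

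Section 5.6 opens with "Patients will be followed for 2 years after completion of chemoradiation or until death, whichever occurs first, for toxicity and PFS" and ends with "Patients removed from study for unacceptable adverse event(s) will be followed until resolution or stabilization of the adverse event". Between the two, it passes patients to registry follow-up once toxicity has resolved and the study team has completed the primary endpoint assessment.

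Other sections expect observation to continue after treatment stops. Calendar footnotes e and h set scans and examinations at least every 6 months for two years, with no exception for removed patients. Section 11.1.4.3 says of patients who stop for symptomatic deterioration: "Every effort should be made to document the objective progression even after discontinuation of treatment". Section 13.7.2 wants response assessed in all patients despite major treatment deviations.

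On analysis, Section 11.1.1 says "All patients will be evaluable for toxicity from the time of their first treatment with cisplatin" and Section 13.7.1 says "All patients will be evaluable for toxicity from the time of their first treatment with cisplatin or radiation". Section 13.2 says "Conservatively assuming a 10% loss to follow-up, we will recruit 80 total patients for at least 72 analyzable". Section 13.4 tests toxicity and 2-year local control as proportions with Fisher's exact test.

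**The concern.** Four of the five criteria in 5.5 are not a patient's decision to leave, and several are tied to outcome: progression, toxicity, decline. If meeting one ends observation, data are lost in relation to the endpoints being compared.

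Section 5.6 does not repair this. Its only provision for removed patients covers adverse-event removals and may end well before two years. Its general 2-year period is counted from an event that a patient who stops early may never have.

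The analysis sections have no fallback. Every treated patient is evaluable for toxicity, yet nothing says how to classify someone with no recorded event and fewer than 90 days of observation. Section 13.7.2 counts unknown response as failure, but that covers response only, which is not assessed in Cohort 2. Nothing is said about unknown local-control status at two years.

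**Working it through.** **1. The plan's own figures.** Inputs from Section 13.2: toxicity 80% (every 3 weeks) and 50% (weekly), 36 per arm, one-sided 0.05, Fisher's exact test. Power is the sum, over all pairs of event counts (x1, x2) with one-sided Fisher p ≤ 0.05, of Bin(x1; 36, 0.80) × Bin(x2; 36, 0.50). The result is 80.9%, which reproduces the stated 80%. Recruitment: 72 / 0.90 = 80, also reproduced. The sample size is not in dispute.

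**2. How much of the primary window is at risk.** Treatment lasts 7 weeks, so removal during the course (by day 49) leaves at least 90 − 49 = 41 of the 90 days unobserved, if removal ends observation. Only patients without a listed event by then can change status.

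**3. Effect on power of missed events.** The documents give no loss rate, so these are assumptions. The 36 per arm is already net of the 10% allowance; the 40-per-arm column keeps everyone in the denominator.

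| Observed rates, every 3 weeks v weekly | Assumption | 36 per arm | 40 per arm |
|---|---|---|---|
| 80 v 50 | nothing missed | 80.9% | 83.7% |
| 76 v 47.5 | 5% of events missed in both arms | 76.0% | 77.5% |
| 72 v 45 | 10% of events missed in both arms | 71.2% | 71.5% |
| 77.5 v 47.5 | 2.5 points missed in both arms | 80.3% | 82.1% |
| 75 v 45 | 5 points missed in both arms | 79.9% | 80.9% |

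Proportional loss shrinks the difference (72 − 45 = 27 points instead of 30) and costs power. Equal absolute loss leaves the difference at 30 points and costs little.

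**4. Does the unstated classification rule matter?** Take the planned 10% loss as 4 of 40 patients per arm with unknown status, and suppose 29/36 v 18/36 events are observed. One-sided Fisher p-values:

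- Complete cases: 0.006.
- All unknowns counted as non-events (29/40 v 18/40): 0.011.
- All unknowns counted as events (33/40 v 22/40): 0.007.
- Least favourable to weekly (29/40 v 22/40): 0.081.
- Most favourable to weekly (33/40 v 18/40): 0.0005.

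The same rule in both arms leaves this example below 0.05; only the extreme opposite assignment crosses it.

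**5. Two-year local control.** With 40 per arm, each unknown patient moves an arm's rate by up to 1/40 = 2.5 points. Counting all unknowns as controlled instead of failed shifts the between-arm difference by k/40, where k is the imbalance in unknowns: 0 if equal, 2/40 = 5 points for two patients, 4/40 = 10 points for four.

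**The case against.** The best reply is that this is loose terminology. Section 5.7 does not say that data collection stops. Section 5.6 speaks of removed patients who are nevertheless followed, and its first sentence names death as the only earlier end to the two years. It also expects the study team to complete the primary endpoint assessment. Section 7.6 requires all adverse events, apart from listed exclusions, in routine submissions without excepting removed patients; the calendar's adverse-event row runs into follow-up; and footnote g sets a questionnaire point at 3 months (± 6 weeks) from initiation of treatment. All of this favours reading 5.7 as meaning off treatment, and it stands as evidence of intent. It does not settle the text: 5.7 is headed as removal from study, and the last sentence of 5.6 gives adverse-event removals a shorter follow-up of their own.

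The reply is also right that the exposure is limited. Progression is itself a PFS event, and local progression settles local-control status. Section 13.4 calls the secondary endpoints exploratory.

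A reader might infer more: that the protocol ends all data collection at treatment discontinuation, or that the primary comparison is biased or underpowered. The documents support neither. Losses confined to one arm would cost more power than the table shows, but nothing in the documents indicates such an imbalance. Nor is every cisplatin stop a removal: permanent discontinuation of cisplatin under Section 6 is not named in 5.5, and whether it triggers 5.7 is unclear.

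**Conclusion.** The contradiction is real and should be corrected. Section 5.7 and the last sentence of 5.6 cannot be applied literally alongside the rest of 5.6, calendar footnotes e and h, 11.1.4.3 and 13.7.2. The consequence is a risk, not a demonstrated loss: it arises if sites act on the wording of 5.7.

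The risk falls mainly on 2-year local control, late toxicity, the questionnaires, and PFS in patients removed without progression. For the primary endpoint an effect is possible but not shown. Power stays near 80% or falls to about 71% depending on which assumed loss pattern holds, and none of those patterns comes from the documents. Separately, the absence of a rule for incomplete 90-day toxicity and unknown 2-year local control is a gap in Section 13.4 whichever way 5.7 is read.

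**What to change.** **Protocol.** Leave the 5.5 criteria unchanged. Reconcile 5.5 to 5.7 so that meeting a criterion ends protocol treatment only. Adverse-event collection to day 90 and the existing calendar follow-up to 2 years then continue unless the patient withdraws consent to follow-up. Give the 2-year clock an origin that patients who stop early also have. End or discontinuation of treatment would serve. So would start of treatment, which 11.1.6 already uses for PFS, but that shortens follow-up for completers by about 6-7 weeks. Make follow-up of an adverse event to resolution or stabilization additional to the 2 years.

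**Section 13.4.** Estimate 2-year local control with a time-to-event method that censors incomplete follow-up, and state how death without local failure is handled. Report by arm the number of event-free patients with under 90 days of observation. Repeat the primary test counting them all as events and then all as non-events.

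**Cost.** Wording changes, a few extra follow-up contacts for patients who stop early, and a little more analysis. No treatment rule changes. The change is best made before follow-up accrues, since observations not made after removal may not be recoverable.
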